#### smallest sum LD since the treatment started

#### 11.5.2 Evaluation of Best Overall Response

The best overall response is the best response recorded from the start of the treatment until disease progression/recurrence (taking as reference for progressive disease the smallest measurements recorded since the treatment started). Best overall response will be based on the overall response of the *Non-targeted* lesions.

#### 11.5.3 Duration of Response

Response will be defined as evidence of CR, PR, or stable disease. The duration of response will be measured from the start of treatment until the criteria for progression are met.

Duration of CR or PR: The duration of CR or PR will be recorded from the time measurement criteria are met for CR or PR (whichever is first recorded) until the first date that current or progressive disease is objectively documented (taking as reference for progressive disease the smallest measurements recorded since the treatment started).

Duration of Stable Disease: Stable disease is measured from the start of the treatment and must be at least 6 months in duration or until the criteria for progression are met, taking as reference the smallest measurements recorded since the treatment started.

#### 11.5.4 Clinical Response Parameters

**Time to Local Progression (TTLP)** is defined as the elapsed time from the start of treatment to the date of documented local progression or death, whichever happens earliest.

**Progression-Free Survival (PFS)** is defined is the time from starting treatment to the time of first documented tumor progression or death due to any cause, whichever occurs first. Death is considered as an event here. For subjects whose disease does not progress or who do not die, PFS will be censored at the time of the last visit.

*Time to Progression (TTP)* is defined as the time from starting treatment to the time of first documented tumor progression. Subjects who do not progress will be censored at the time of the last contact. In addition, death from any cause will also be censored.

Overall Survival (OS) is defined as the time from starting treatment until death due to any cause. For subjects who do not die, time to death will be censored at the time of last contact.

**Locoregional Control (LRC)** is defined as the time from starting treatment until local and/or regional relapse is documented

#### 11.5.5 Response Review

All responses will be reviewed by the study co-investigator radiologist.

### 12 ADVERSE EVENT REPORTING REQUIREMENTS

#### 12.1 General

Adverse event collection and reporting is a routine part of every clinical trial. This study will use the descriptions and grading scales found in the NCI Common Terminology Criteria for Adverse Events version 4.0 (CTCAE v 4.0) that is available at http://ctep.cancer.gov/reporting//ctc.html.

Information on all Grade 3 or greater adverse events, whether reported by the participant, directly observed, or detected by physical examination, laboratory test or other means, will be collected, recorded, followed and reported as described in the following sections. In addition, grade 1 and 2 adverse events treated with concomitant medicine/procedure or deemed to be of clinical significance by a study investigator will be collected, recorded, followed and reported as described in the following sections.

Participants should be instructed to report any serious post-study event(s) that might reasonably be related to participation in this study. The investigator should notify the IRB and any other applicable regulatory agency of any unanticipated death or adverse event occurring after a participant has discontinued or terminated study participation that may reasonably be related to the study.

#### 12.2 Definitions

#### 12.2.1 Adverse Event (AE)

An adverse event is any undesirable sign, symptom or medical condition or experience that develops or worsens in severity after starting the first dose of study treatment or any procedure specified in the protocol, even if the event is not considered to be related to the study.

Abnormal laboratory values or diagnostic test results constitute adverse events only if they induce clinical signs or symptoms or require treatment or further diagnostic tests.

For this Phase II study only Grade 3 or higher adverse events, or grade 1 and 2 adverse events treated with concomitant medicine/procedure, or grade 1 and 2 adverse events deemed to be of clinical significance by a study investigator will be collected.

#### 12.2.2 Serious adverse event (SAE)

A serious adverse event is an undesirable sign, symptom, or medical condition which:

- is fatal or life-threatening;
- requires or prolongs inpatient hospitalization;
- results in persistent or significant disability/incapacity;
- constitutes a congenital anomaly or birth defect; or
- jeopardizes the participant and requires medical or surgical intervention to prevent one of the outcomes listed above.

Events **not** considered to be serious adverse events are hospitalizations for:

- routine treatment or monitoring of the studied indication, not associated with any deterioration in condition, or for elective procedures
- elective or pre-planned treatment for a pre-existing condition that did not worsen
- emergency outpatient treatment for an event not fulfilling the serious criteria outlined above and not resulting in inpatient admission
- respite care

#### 12.2.3 Expectedness

- Expected: Expected adverse events are those that have been previously identified as resulting from administration of the agent. For the purposes of this study, an adverse event is considered expected when it appears in the current adverse event list, the Investigator's Brochure, the package insert or is included in the informed consent document as a potential risk.
- Unexpected: An adverse event is considered unexpected when it varies in nature, intensity or frequency from information provided in the current adverse event list, the Investigator's Brochure, the package insert or when it is not included in the informed consent document as a potential risk

#### 12.2.4 Attribution

Attribution is the relationship between an adverse event or serious adverse event and the study treatment. Attribution will be assigned as follows:

- Definite The AE is clearly related to the study treatment.
- Probable The AE is likely related to the study treatment.
- Possible The AE may be related to the study treatment.
- Unlikely The AE is doubtfully related to the study treatment.
- Unrelated The AE is clearly NOT related to the study treatment.

#### 12.3 Potential Adverse Events

Signs and symptoms of disease progression are not considered AEs. The development of a new cancer should be regarded as an AE. New cancers are those that are not the primary reason for administration of study treatment and have been

identified after inclusion of the patient into the clinical study.

Because patients are receiving standard treatments, which are not part of this study, their treating physician will be counseling them on the risk of their treatments, including the risk of surgery, radiation therapy, and/or chemotherapy, whichever is appropriate for the type and the stage of their cancer. The procedures related to the study are phlebotomy, PET imaging (all are optional), SBRT, and CBI administration.

Phlebotomy can cause pain, bleeding, and rare needle site infection. PET imaging results in low dose radiation exposure (see Investigator's Brochure for details of dosimetry), which has an extremely small risk of causing a secondary cancer.

#### 12.4 Stereotactic Body Radiation Treatment

It is difficult at this time to predict with confidence the complication rate from the proposed SBRT; however, it is reasonable to extrapolate from the current experience and reported literature with SBRT. One significant toxicity is radiation pneumonitis, which can be manifested as fever, increased excertional dypsnea, pleuritic chest pain, and peritumoral infiltrate on chest imaging. It generally occurs between 1 to 3 months of completion of radiotherapy. The risk of grade 2-4 radiation pneumonitis is aproximately 10-15% in patients treated with standard fractionated large field radiotherapy and higher in patients treated with combined chemoradiotherapy. It is highly dependent on the volume of the lung treated to high dose and the mean lung dose. At this point, the incidence of RT pneumonitis from SBRT combined with immunotherapy for small pulmonary tumors is unknown. However, if the treated tumor volume is kept  $\leq 65$  cc, the risk should be <10-15% with the proposed dose level.

Other toxicities commonly associated with such treatment includes colitis, diarrhea, hypophysitis, rash, arthritis, fatigue, nausea, vomiting, anorexia, and weight loss. Some of these symptoms can also be due to tumor progression. Clinical and radiographic assessments will be performed as indicated to identify all adverse effects, ascertain their etiology, and provide the most appropriate palliative measures. Complications orther than radiation pneumonitis, if any, will be graded according to the Common Toxicity Criteria, National Cancer Institute, version 4.0.

#### 12.5 Reporting Procedures

#### 12.5.1 **General**

Adverse events will be recorded at each visit. If an adverse event requiring medical attention occurs between visits, this will be recorded as well. The variables to be recorded for each adverse event include, but are not limited to, onset, resolution, intensity, action taken, outcome, causality rating and whether it constitutes an SAE or not. The intensity of the adverse event should be captured using CTCAE criteria, version 4.0, when possible.

Pregnancy in itself is not reported as an AE unless there is a suspicion that an investigational product may have interfered with the effectiveness of a contraceptive medication.

All adverse events will be captured on the appropriate study-specific case report forms (CRFs).

#### 12.5.2 Institutional Review Board

All adverse events and serious adverse events will be reported to the IRB per current institutional standards. If an adverse event requires modification of the informed consent, these modifications will be provided to the IRB with the report of the adverse event. If an adverse event requires modification to the study protocol, these modifications will be provided to the IRB as soon as is possible.

#### 13 DATA AND SAFETY MONITORING PLAN

Data and safety monitoring oversight will be conducted by the UCSD Moores Cancer Center Safety Monitoring Committee at the University of California at San Diego. All reportable anticipated and unanticipated protocol events/problems and amendments that are submitted to the IRB will also be reviewed by the Safety Monitoring Committee Chair (or designee) and QA manager.

#### 14 REGULATORY CONSIDERATIONS

#### 14.1 Protocol Review and Amendments

Information regarding study conduct and progress will be reported to the Institutional Review Board (IRB) per the current institutional standards.

Any changes to the protocol will be made in the form of an amendment and must be approved by the IRB prior to implementation.

#### 14.2 Informed Consent

The investigator (or his/her designee) will explain to each subject the nature of the study, its purpose, the procedures involved, the expected duration, the potential risks and benefits involved and any discomfort it may entail. Each subject will be informed that participation in the study is voluntary, that she may withdraw from the study at any time, and that withdrawal of consent will not affect her subsequent medical treatment or relationship with the treating physician(s) or institution. The informed consent will be given by means of a standard written statement, written in non-technical language, which will be IRB approved. The

subject should read and consider the statement before signing and dating it, and will be given a copy of the document. No subject will enter the study or have study-specific procedures done before his/her informed consent has been obtained.

In accordance with the Health Information Portability and Accountability Act (HIPAA), the written informed consent document (or a separate document to be given in conjunction with the consent document) will include a subject authorization to release medical information to the study sponsor and supporting agencies and/or allow these bodies, a regulatory authority, or Institutional Review Board access to subjects' medical information that includes all hospital records relevant to the study, including subjects' medical history.

#### 14.3 Ethics and GCP

This study will be carried out in compliance with the protocol and Good Clinical Practice, as described in:

- 1. ICH Harmonized Tripartite Guidelines for Good Clinical Practice 1996.
- 2. US 21 Code of Federal Regulations dealing with clinical studies (including parts 50 and 56 concerning informed consent and IRB regulations).
- 3. Declaration of Helsinki, concerning medical research in humans (Recommendations Guiding Physicians in Biomedical Research Involving Human Subjects, Helsinki 1964, amended Tokyo 1975, Venice 1983, Hong Kong 1989, Somerset West 1996).

The investigators agree to adhere to the instructions and procedures described in it and thereby to adhere to the principles of Good Clinical Practice that it conforms to.

#### 15 STATISTICAL CONSIDERATIONS

#### 15.1 Endpoints

#### 15.1.1 Primary Objectives

To determine whether SBRT combined with concurrent CBI improves the objective response rate compared to CBI alone in patients with metastatic disease.

#### 15.1.2 Secondary Objectives

- To assess the safety and toxicity of CBI used concurrently with SBRT delivered in the population enrolled using grading with CTCAE v. 4.0
- O To assess progression free survival and overall survival in patients after completion of SBRT in combination with CBI. Progression-free survival will be measured from time of enrollment to date of disease progression or death. Patients who are lost to follow-up will be censored for determination of progression-free survival on the date of their last evaluation. Overall survival is defined as time from enrollment to death

due to any cause.

- o To assess the rates of stable disease great than or equal to 6 months during and after SBRT in combination with CBI compared to CBI alone
- o To determine whether SBRT combined with concurrent CBI results improvements in anti-tumor immune responses compared to CBI alone

#### 15.2 Sample Size/Accrual Rate

The primary endpoint will be objective response rate at 16 weeks. The treatment regimen would be considered of insufficient activity for further study in this population if the 16 week objective response is 10% less than historical controls.

The objective response rate to CBI monotherapy depends on disease type and is reported to be approximately 40% in melanoma and 20-25% in NSCLC. Dual agent checkpoint blockade has recently been shown to have a response rate of 61% in Metastatic melanoma. In order to detect a cumulative relative 33% increase in objective response rate [i.e. from 61% to 81% (for dual agent), 40% to 53% for single agent in melanoma, and 25% to 33% in NSCLC] with a one tailed p value <0.05% with 80% power incorporating the respective frequencies of tumor types this would require 146 patients total.

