# 1. PROTOCOL SYNOPSIS

TITLE	Randomized Phase II Study of Checkpoint Blockade Immunotherapy combined with Stereotactic Body Radiation Therapy in Advanced Metastatic Disease.
STUDY PHASE	Phase II
INDICATION	Patients who will receive CBI immunotherapy with at least 1 site of measurable metastatic disease which will not be irradiated.
PRIMARY OBJECTIVE	To determine whether SBRT combined with concurrent CBI improves the relative objective response rate (CR+PR) compared to CBI alone in patients with metastatic disease.
SECONDARY OBJECTIVES	
 
To assess the safety and toxicity of CBI used concurrently with SBRT delivered in 3 fractions in patients with metastatic disease
 
To determine the progression free survival, overall survival, and rate of stable disease greater than or equal to 6 months in patients after completion of SBRT in combination with CBI
 
To assess whether SBRT combined with concurrent CBI results in improvements in anti-tumor immune responses compared to CBI alone
 

HYPOTHESIS	Concurrent SBRT and CBI will increase the relative objective response (CR+PR) rate by at least 33% compared to CBI alone.
STUDY DESIGN	Patients who will receive CBI and have at least 1 site of measurable metastatic disease which will not be irradiated will be candidates for study. Patients will be randomized (1:1) to CBI combined with SBRT or CBI alone. SBRT at 9.5Gy x3 fractions will be delivered within 1-21 days of the start of Cycle #1 of CBI. The first six patients will be treated and observed for toxicity in the safety run-in phase for 30 days after radiation before continuing with further accrual. Radiation dose reduction is allowed if necessary to meet tissue constraints (6Gyx3 Minimum Dose). Response rates will be determined from the non-irradiated lesion/lesions and three blood draws will be obtained to analyze anti-tumor immune responses.
SAMPLE SIZE BY TREATMENT GROUP	73 patients per group (146 patients total)

SUMMARY OF SUBJECT ELIGIBILITY CRITERIA	
 
At least 1 site of measurable metastatic disease which will not be irradiated.
 
Plan to treat patient with CBI
 
Age ≥3 years.
 
Lansky scale score of ≥70 (ages ≥ 3 or < 16 years)         OR         Karnofsky scale score of ≥70 (ages ≥ 16 or < 18 years)         OR         ECOG performance status ≤ 2 (18 years or older).
 
Histologic confirmation of malignancy (primary or metastatic tumor).
 

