CBI PRODUCT DOSAGE AND ADMINISTRATION	Commercially available checkpoint blockade immunotherapy will be administered intravenously as clinically indicated.
CONTROL GROUP	CBI Alone
PROCEDURES	1. Physical exam 2. Three Research Blood draws 3. CT or MRI of Involved Site 4. PET-CT (optional) 5. SBRT 6. IV CBI administration

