#### 5. PARTICIPANT SELECTION AND ENROLLEMENT CRITERION

#### 5.1 Inclusion Criteria

- 5.1.1 The PI or Co-Investigator Radiation Oncologist states that one of the lesions can be treated with SBRT.
- 5.1.2 Patient must have at least 1 site of measurable disease by Response Evaluation Criteria in Solid Tumors (RECIST) 1.1 criteria on computed tomography (CT) or Magnetic resonance imaging (MRI) which will not be irradiated.
- 5.1.3 Histological confirmation of malignancy (primary or metastatic tumor).
- 5.1.4 Patient may have any prior therapy allowed aside from having had prior radiotherapy to the treatment site (see exclusion criteria 5.2.3).
- 5.1.5 Patient must be  $\geq 3$  years of age.
- 5.1.6 Lansky scale score of  $\geq$ 70 (ages  $\geq$  3 or < 16 years) OR Karnofsky scale score of  $\geq$ 70 (ages  $\geq$  16 or < 18 years) OR ECOG performance status  $\leq$  2 (18 years or older).
- 5.1.7 Patient's screening laboratory values must meet the following criteria:

Leukocytes $\geq 2,000/\mu L$ Absolute Neutrophil Count $\geq 1,000/\mu L$ Platelets $\geq 50,000/\mu L$ 

Total bilirubin \leq 2x institutional upper limit of normal
AST(SGOT)/ALT(SGPT) <2.5 X institutional upper limit of

normal

Serum creatinine  $\leq 1.5x$  ULN or creatinine clearance  $(CrCl) \geq 40$  mL/min (using the

Cockcroft-Gault formula):

- (1) Female CrCl = (140 age in years) x weight in kg x 0.85 /72 x serum creatinine in mg/dL
- (2) Male CrCl = (140 age in years) x weight in kg x 1.00/72 x serum creatinine in mg/dL

Pulse Oximetry

≥92% on Room Air at Rest

- 5.1.8 Patient or parent/legal guardian must have the ability to understand and the willingness to sign a written informed consent document.
- 5.1.9 For Patients <18 years of age, enrollment on trial and potential for use of CBI or CBI combined with SBRT must be agreed upon by consensus opinion of a multidisciplinary pediatric tumor board.

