#### 7.2.4 Nivolumab combined with Ipilimumab Dosing

Nivolumab combined with Ipilimumab will be dosed and scheduled according to FDA approved labels or per institutional guidelines at discretion of treating medical oncologist. For additional details regarding drug storage, preparation, and combination administration please refer to Nivolumab package insert[85]

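### Section 15.2 claims 80% power for a tumour-weighted pooled gain without giving the weights, pooled rates or test; on its own rates, 73 per arm gives 80% only if a large majority of patients respond at dual-agent rates

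*Combined protocol and SAP*

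**What the plan says.** Section 15.2 sets the target as follows: "In order to detect a cumulative relative 33% increase in objective response rate". It gives three pairs of rates: "i.e. from 61% to 81% (for dual agent), 40% to 53% for single agent in melanoma, and 25% to 33% in NSCLC". It then closes the calculation: "with a one tailed p value <0.05% with 80% power incorporating the respective frequencies of tumor types this would require 146 patients total". The same section gives the NSCLC control rate as a range, 20-25%, and uses the upper end. It quotes the 61% rate for dual-agent treatment in metastatic melanoma.

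The synopsis gives "73 patients per group (146 patients total" and the allocation: "Patients will be randomized (1:1) to CBI combined with SBRT or CBI alone". It names no stratification factor. Section 15.5 describes the primary comparison but names no test.

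On who may enter, 5.1 asks for "Histological confirmation of malignancy (primary or metastatic tumor", without restricting tumour type. On treatment, the synopsis says: "Commercially available checkpoint blockade immunotherapy will be administered intravenously as clinically indicated".

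**The concern.** The three settings differ greatly in how many patients they need, so the power of a pooled comparison depends mainly on the mix. Section 15.2 says the mix was taken into account but does not say what it was. It also leaves out the weighted control and treatment rates and the test. A reader therefore cannot reproduce 146 as described, and cannot tell whether 80% applies to the population that the protocol will enrol.

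This is the only power statement for the primary endpoint, and it carries no qualification. If the real mix is less favourable than the one assumed, a non-significant result is more likely than the stated one in five even when the hypothesised gain is real. It could then be misread as evidence that SBRT adds nothing.

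**Working it through.** **Inputs.** From 15.2: rate pairs 0.61/0.81 (dual-agent), 0.40/0.53 (single-agent melanoma), 0.25/0.33 (NSCLC); one-sided test; 80% power. From the synopsis: 1:1 allocation, n = 73 per arm. Assumed: alpha 0.05, and the tumour mixes, since none is stated.

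**Formulas.** With p̄ = (p1+p2)/2 and d = p2−p1:

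- n per arm = [1.645·√(2p̄(1−p̄)) + 0.842·√(p1(1−p1)+p2(1−p2))]² / d²
- continuity-corrected n = (n/4)·[1+√(1+4/(n·d))]²
- power = Φ{[d − 1.645·√(2p̄(1−p̄)/73)] / √((p1(1−p1)+p2(1−p2))/73)}; for the corrected test, replace d in the numerator by d − 1/73
- tumour-stratified (Mantel-Haenszel) power = Φ[(E − 1.645·√V0)/√V1]. Here, summing over strata with m = 73 × share, E = Σ m·d/2, V0 = Σ m·p̄(1−p̄)/2 and V1 = Σ m·[p1(1−p1)+p2(1−p2)]/4.

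**Step 1: the plan's figure.** The weighted 146 cannot be rebuilt, because the weights are missing. For 61% vs 81% alone, p̄ = 0.71 and n = (1.056+0.527)²/0.04 = 62.6. The corrected n is 15.65 × (1+√1.32)² = 72.2, so 73 per arm and 146 in total. Two other calculations bear on where 146 came from. An exact target of 0.61 × 1.33 = 0.8113 gives 71.3 corrected, so 72 per arm. A mix of 87% dual-agent and 13% single-agent melanoma (0.583 vs 0.774) gives 73.0 uncorrected.

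**Step 2: each setting alone, 73 per arm.**

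| Rates | n per arm, uncorrected / corrected | Power, uncorrected / corrected |
|---|---|---|
| 61 vs 81% | 62.6 / 72.2 | 85% / 80% |
| 40 vs 53% | 181.0 / 196.1 | 47% / 41% |
| 25 vs 33% | 396.8 / 421.4 | 28% / 22% |
| 20 vs 26.6% (20% × 1.33) | 506.2 / 536.1 | 24% / 18% |

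**Step 3: illustrative mixes** (dual-agent / single-agent melanoma / NSCLC). For equal thirds, p1 = (0.61+0.40+0.25)/3 = 0.420 and p2 = (0.81+0.53+0.33)/3 = 0.557.

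- Unstratified: (0.1367 − 0.1361)/0.0820 = 0.007, so power is 50.3%. Corrected: (0.1230 − 0.1361)/0.0820 = −0.16, so 43.6%.
- Stratified: E = 4.99, V0 = 8.04, V1 = 7.84, so power is 54.6%.

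| Mix | Pooled rates | Unstratified corrected | Unstratified uncorrected | Stratified uncorrected |
|---|---|---|---|---|
| Equal thirds | 0.420 vs 0.557 | 44% | 50% | 55% |
| 50/25/25 | 0.468 vs 0.620 | 52% | 58% | 63% |
| 70/15/15 | 0.524 vs 0.696 | 62% | 69% | 73% |
| 84/16/0 | 0.576 vs 0.765 | 73% | 79% | 80% |

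With NSCLC at 20% vs 26.6%, the same formulas give 42-54%, 50-63% and 61-73% for the first three mixes.

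**Step 4: dual-agent share needed for 80% power.** Each range runs from a remainder that is all single-agent melanoma to one that is all NSCLC.

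| Test | Share needed |
|---|---|
| Stratified, uncorrected | 84-88% |
| Unstratified, uncorrected | 87-92% |
| Fisher's exact | 98-99% |
| Continuity-corrected, stratified or not | about 99% |
| Stratum weights chosen to maximise power | 74-83% |

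With unrounded gains and a melanoma remainder, the 84% becomes 82% (×1.33) or 80% (×4/3). That gives the overall range of roughly 80-92% for uncorrected tests.

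**Step 5: the significance level.** Taken literally as 0.0005, 61% vs 81% alone would need 174.0 per arm uncorrected (183.9 corrected), and 73 per arm would give 26% power. A slip for 0.05 is the sensible reading.

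**The case against.** The strongest reply is that no wrong sum has been shown. Section 15.2 says frequencies were used, and at least one mix (87/13/0, uncorrected) gives exactly 73 per arm. The sponsor may hold weights that justify 80%. That stands: the defect is an undocumented assumption on which the claim depends heavily, and stating suitable weights would resolve it.

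Three further points also stand. There is no sharp cut-off at 84%: the threshold moves with rounding and test, and the stratified test still has 79% power at 80/20/0 and 77% at 75/25/0. The mixes in step 3 are assumptions, so the true shortfall is unknown. The calculation covers only the settings with rates in 15.2, although other histologies may enrol.

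Two stronger readings are tempting but unsupported. A reader might infer that 146 was computed from the dual-agent pair alone and the weighting ignored. The match is suggestive, but step 1 shows another route to 73, and the exact 1.33 target gives 72. A reader might also note that one of the seven regimen dosing sections in chapter 7 is for a combination ("Nivolumab combined with Ipilimumab will be dosed and scheduled according to FDA approved labels") and conclude that dual-agent patients will be few. A count of sections says nothing about enrolment. Open eligibility and regimen choice show only that the mix is not controlled.

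That this is phase II does not answer the point, because the trial makes a randomised comparison and states its power without qualification.

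**Conclusion.** The power statement cannot stand as written. It omits the inputs that determine it. On the section's own rates, it is true only if a large majority of patients, roughly 80-92% under uncorrected tests and more under conservative ones, respond at dual-agent rates. Nothing in the plan secures that. Under the illustrative mixes, power lies between 44% and 73%, and somewhat lower if the NSCLC control rate is 20%.

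This rests on one-sided 0.05, 73 evaluable patients per arm, the rate pairs in 15.2 and, for the mix-specific figures, assumed shares. A reader might go further and conclude that the trial is shown to be underpowered, or will miss a real gain at some particular rate. The documents do not support that, because they do not give the mix.

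**What to change.** In 15.2, with a matching line in the synopsis:

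1. State the assumed tumour and regimen mix, and the weighted control and treatment response rates behind 146.
2. Name the primary test and say whether it is stratified by tumour type or regimen.
3. Replace the unqualified 80% with the power that this mix and test give at 73 per arm. Keep 80% only if they deliver it.
4. Correct the significance level to one-sided p<0.05.

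Optionally, list the single-setting powers from step 2 as scenarios, including the 20% NSCLC rate. They are not planned separate analyses and should be labelled accordingly.

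The cost is wording only, with no added patients or procedures. The drawback is that the stated power may look less favourable. The trial becomes no larger, so a negative result would have to be read with that power in mind.

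### Section 15.2 prints the only significance level for the primary comparison as 0.05% (0.0005), almost certainly a slip for 0.05; at the printed level 146 patients do not give 80% power

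*Combined protocol and SAP*

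**What the plan says.** The trial compares two arms on a binary outcome. The synopsis states "Patients will be randomized (1:1) to CBI combined with SBRT or CBI alone", with 73 patients in each group. Section 15.2 adds "The primary endpoint will be objective response rate at 16 weeks".

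The sample size sentence in 15.2 begins "In order to detect a cumulative relative 33% increase in objective response rate" and lists three pairs of rates: "from 61% to 81% (for dual agent), 40% to 53% for single agent in melanoma, and 25% to 33% in NSCLC". It sets the error rates as "with a one tailed p value <0.05% with 80% power" and says that the total of 146 was reached "incorporating the respective frequencies of tumor types". Those frequencies are not given.

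No other section states a significance level for this comparison. Section 15.5, on the primary analysis, defines response and an analysis population but names neither a test nor a threshold. Section 15.6 mentions statistical significance for the immune endpoints without a level, and its 95% intervals belong to the time-to-event summaries. The rule in 15.2 on insufficient activity relative to historical controls is not a significance level.

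**The concern.** A threshold of 0.05% is 0.0005, which is 100 times stricter than 0.05 (0.05 / 0.0005 = 100). Because 15.5 is silent, the figure in 15.2 is the only threshold a reader can find for the primary comparison.

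Two things are at stake. The sentence contradicts itself if the printed level cannot deliver 80% power with 146 patients. And a result with a p-value between 0.0005 and 0.05 would fail the printed level but pass the level probably meant. Choosing between the two after the data are seen is what a pre-specified threshold should prevent.

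**Working it through.** **Inputs.** From 15.2: one-sided test, 80% power, and the pairs 61%/81%, 40%/53% and 25%/33%. From the synopsis: 1:1 allocation and n = 73 per arm. No allowance for dropout is stated. The choice of formula is mine, because the plan names none.

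**Formulas.** Let d = p2 − p1, p̄ = (p1 + p2)/2, V0 = 2p̄(1 − p̄) and V1 = p1(1 − p1) + p2(1 − p2).

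- Size per arm: n = (z_α√V0 + z_β√V1)² / d²
- With continuity correction: n' = (n/4)·(1 + √(1 + 4/(n·d)))²
- Power: Φ[(d√n − z_α√V0) / √V1]

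Here z_β = 0.842. For one-sided 0.05, z_α = 1.645; for one-sided 0.0005, z_α = 3.291.

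**Step 1: the plan's own figure.** For 61% vs 81%: d = 0.20, p̄ = 0.71, √V0 = 0.6417, √V1 = 0.6259. At one-sided 0.05:

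- n = (1.645 × 0.6417 + 0.842 × 0.6259)² / 0.04 = 62.6, so 63 per arm (126 in total).
- n' = (62.6/4)·(1 + √(1 + 4/(62.6 × 0.20)))² = 72.2, so 73 per arm (146 in total).

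The stated total is matched. At one-sided 0.0005 the same pair needs 175 per arm, or 184 with correction (350 or 368 in total).

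**Step 2: power at the printed level, 73 per arm.** For 61% vs 81%, d√n = 0.20 × 8.544 = 1.709. Power is Φ[(1.709 − 3.291 × 0.6417)/0.6259] = Φ(−0.643) = 26%.

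**Step 3: all pairs at both levels** (no continuity correction unless stated).

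| Pair | Power at 0.0005 | Power at 0.05 | Total N for 80% at 0.0005 (corrected) | Total N for 80% at 0.05 (corrected) |
|---|---|---|---|---|
| 61% vs 81% | 26% | 85% | 350 (368) | 126 (146) |
| 40% vs 53% | 4% | 47% | 1,002 (1,034) | 362 (394) |
| 25% vs 33% | 1% | 28% | 2,194 (2,244) | 794 (844) |

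With continuity correction, power at 0.0005 is 20%, 3% and 1%. At 0.05 it is 80%, 41% and 22%.

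**Step 4: mixtures.** The shares of the three groups are not given, so I varied each from 0 to 100%, using both pooled and stratified variance. At 0.0005 the highest power is 26%, when every patient is in the dual-agent group. An equal three-way mix (an assumption; 42.0% vs 55.7%) has about 5% power at 0.0005. At 0.05 it has 50% and would need 330 patients.

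**Step 5: the observed difference needed.** With a control rate of 61%, the smallest significant difference (uncorrected) is 12.8 percentage points at 0.05 and 24.2 at 0.0005. In whole patients, against 45/73 control responders, the SBRT arm would need 55/73 at 0.05 and 63/73 at 0.0005.

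**The case against.** The strongest reply is that this is a stray percent sign which almost any statistician would read as 0.05, and that the low power figures describe a design nobody planned. That largely stands, and it lowers the weight of the point. It does not remove the point, because no other sentence overrides the printed figure and the reader has to infer the intended level.

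A second reply is that the figure is an input to a sample size sentence, not a declared decision rule. That is fair: 15.5 contains no decision rule at all. The gap supports stating the level there.

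A reader might also draw three stronger conclusions that the documents do not support:

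- *That a 0.0005 rule was intended.* The agreement with 73 per arm at 0.05 points the other way.
- *That the trial has almost no chance of success for most of its patients.* The frequencies of the groups are not given, so nothing shows which group is the majority. In the dual-agent group, power at the printed level is 26%, which is low but not negligible.
- *That 146 was derived from 61% vs 81% alone.* The match is exact, but 15.2 says that the total takes all tumor types into account, and the method is not shown. The match suggests 0.05 without proving how 146 arose. The finding that 0.0005 does not fit rests on firmer ground: no mix reaches 80% at that level.

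**Conclusion.** The point holds as an error in a printed figure, almost certainly typographical. At one-sided 0.0005 with 73 per arm, power is at most 26% in any group or mix, so the stated 80% is false at the printed level. This rests on the 15.2 response rates, 1:1 allocation and a normal-approximation test of two proportions. Continuity correction lowers the maximum to 20% and does not change the conclusion.

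It would be wrong to infer that removing the percent sign makes the power statement true. At one-sided 0.05 the 80% figure holds only if all or nearly all patients (about 90%) are in the dual-agent group. Without correction, a mix of 90% dual-agent and 10% NSCLC gives 78-81%, and 80% dual-agent with 20% single-agent melanoma gives 77-79%. That shortfall is a separate and larger matter than the misprint.

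**What to change.** 1. In 15.2, remove the percent sign so that the level reads one-sided p<0.05.
2. In 15.5, state the same one-sided level as the threshold for the primary test, and name the test.
3. In 15.2, give the assumed share of each of the three groups and the formula used, and restate the power of 146 patients for that mix.

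Items 1 and 2 cost one character and one sentence, with no effect on patients or conduct; they should be in place before the primary analysis. Item 3 needs the assumed frequencies and a short recalculation. If the restated power is well below 80%, the sponsor will have to decide whether to accept it or revisit the sample size, which correcting the threshold does not settle.
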